7.4. Case Report Forms

All assessments, questionnaires, and observations throughout the investigation for each subject must be carefully recorded in an electronic CRF (eCRF). Details about data capture can be found in section 11 (Data Management).

eCRFs will be completed by the Principal Investigator or delegate, who have signed the Site Personnel Signature and Delegation List and Clinical Investigation Training Log. The delegated site personnel will be required to complete e-learning prior to system access. After completed training delegated personnel will receive credentials.

It is the responsibility of the investigator to ensure that all data, all measurements, and observations are entered promptly and correctly and preferably immediately after the subject has been at site or after a phone call. In case this is not possible the data should be entered no later than 7 days after the visit / procedure.

7.5. Concomitant treatment

Concomitant treatment is any medication or medical product which is taken or used during the investigation period.

If other relevant wound care products are required to be used in addition to the study products, as part of standard of care (e.g., barrier cream), this must be documented as well.

Subjects who may require another dressing than the investigational test product(s) (e.g., an antimicrobial dressing superabsorbent dressing or other) will be followed during the four-week investigation period and included in the ITT (intention to treat) analysis but excluded from the PP (per protocol) analysis. The subjects will follow the study procedures except for conformability assessment if possible.

7.6. Supplementary materials and equipment

The Sponsor will provide the Principal Investigators with supplementary materials for the investigation such as computers with access to eCRF if needed and phones with the Medidata eCOA solution installed to obtain photos.

8. Risk - benefit analysis and ethical considerations

8.1. Risk-benefit analysis of the investigational test product

The investigational test products are already CE-marked and will be used according to the IFU.

8.2. Risk-benefit for subjects participating in the clinical investigation

The investigation is conducted in accordance with current law and applicable standards, see section 15. Statement of Compliance. The rights, safety and well-being of human subjects shall prevail over the interest of science of society.

Risks in this investigation are considered equal to the use of other wound care products on the market. Risks associated with the use of wound care products are skin irritation/inflammation, maceration, pain, hyper granulation, and blistering. Section 18 Adverse Events and Adverse Device Effects describe the risks in detail.

There is no known interaction between the use of the investigational test product and the medication that subjects can take. except for what is stated in the exclusion criteria. Disadvantages of testing (trial engagement) may be time spent on visits and responding to questions during visits.

The participating subjects will contribute with important information on the use of wound care products and the socio-economic benefits. Possible benefits for the subjects may be wound healing with fewer products.

8.3. Risk Analysis for the conduct of the clinical investigation

A risk assessment of the clinical investigation will be conducted initially prior to the first subject enrolment and will be periodically re-assessed based on any new risks identified through the process. This assessment will be completed throughout the duration of the investigation, as defined by the study team. A risk-based monitoring strategy may be implemented including on-site remote, and central monitoring. Details of the strategy are defined in the monitoring plan in Section 9.

8.4. Delegation of responsibility

Before initiation of the clinical investigation, sponsor must be provided with key personnel signed and dated curriculum vitae (not more than 2 years old) to verify their qualifications. Key site personnel are those, who treat or evaluate subject data in the clinical investigation. Also, the sponsor will ensure that all site personnel are trained in the investigation procedures, how to complete the eCRFs, procedure for reporting an adverse event or serious adverse event (how, when, to whom), and who to contact in case of emergency related to the investigational device.

9. Monitoring Plan

The sponsor is responsible for ensuring appropriate monitoring of the clinical investigation activities as described below. This study specific monitoring plan includes details regarding the monitoring strategy (i.e., onsite, remote, and centralized).

The clinical monitor will be the primary contact for the PI and delegates.

Monitoring activities are mandatory as per good clinical practice. However, the extend and depth of these activities depend on the criticality of the clinical investigation, speed of enrolment, the experience of the clinical investigation personnel in carrying out clinical investigations and specific study designs.

For the purpose of this clinical investigation the below described monitoring procedures have been selected.

The data collected throughout the investigation and the conduct of the investigation, will be monitored per the monitoring plan to ensure, and verify, that the rights and well-being of the subjects are protected, that the reported data are accurate, complete, and verifiable from source documents, and that the conduct of the investigation complies with the approved CIP, subsequent amendment(s), ISO14155 and the applicable regulatory requirement(s).

The monitoring process is described below.

The monitoring in this investigation will be conducted periodically at all sites by the clinical monitor.

The investigator must be available for and agree to cooperate with Coloplast clinical monitor during their visits and ensure that they have direct access to all documents that they require, including direct access to the subject's files.

The investigation will be subject to internal audits if relevant. All monitoring visits and possible audits will be followed by internal reports and corrective actions, if needed.

Follow-up letters will be forwarded to sites after all visits and any findings should be addressed by the investigator or delegate.

To ensure proper conduct of the investigation, the following visits on site will be performed before/during the investigation:

- Site selection visit
- Site initiation visit
- Periodic monitoring visits
- Close out visits

9.1. Site selection visit

Depending on the prospective clinical investigation sites experience with the specific investigational device, an on-site qualification or site selection visit shall be performed during which the feasibility of the clinical investigation requirements will be discussed and common agreement between sponsor and Principal Investigator shall be reached. This visit may also be replaced by one or more phone calls or conducted remotely, using Microsoft Teams.

9.2. Initiation visit

All clinical investigation sites will complete an initiation visit during which full training on all aspects of the clinical investigation will be provided. The initiation visit will be held as close to the study start as possible.

Before initiation of the clinical investigation, sponsor must be provided with key personnel signed and dated curriculum vitae and documentation of current ISO14155 training (within the last two years) to verify their qualifications.

initiation visit will include training in handling of the investigational products. This visit can also be conducted on-site or remotely if the site is restricting visitors due to the Covid-19 pandemic or other unforeseeable circumstances which may prohibit site visits.

9.3. Monitoring visits

The sponsor shall determine the extent and nature of monitoring appropriate for the clinical investigation based on the risk assessment. The sponsor shall ensure, through oversight of the clinical investigation and timely adverse event reporting, that unanticipated adverse device effects are identified and investigated rapidly so that, where necessary, additional risk control measures can be implemented.

The clinical monitor is to ensure adherence to the clinical investigation plan, the safety of the subjects, accurate data recording on the eCRFs and to monitor recruitment rates and adherence to follow-up schedules. During the clinical investigation, monitors shall check that appropriate written informed consents have been obtained. The Principal Investigator shall permit and assist the monitor to carry out verification of completed eCRFs against data in the source documents.

The principal investigator can delegate tasks to his/her collaborators, however the roles and responsibilities as the time period of involvement for each clinical site personnel must be documented on the Site Personnel signature and Delegation list as well as training received before getting involved with the clinical investigation must be documented in the Clinical Investigation Training Log.

The clinical monitor shall inform the sponsor about any problems relating to facilities, technical equipment or medical staff at the clinical investigation site. The clinical monitor shall also be responsible for notifying such deficiencies in writing to the principal investigator and convene with the clinical investigation site personnel appropriate and timely corrective actions.

The sponsor, or delegate, will provide clinical monitoring, including review of eCRF with verification to the source documentation, as defined in the monitoring plan.

Before doing any review of subject data, the monitor must review the signed Informed Consent Forms and only monitor data from subjects with a correct signature on these forms. The clinical monitor shall also be responsible for notifying such deficiencies in writing to the investigator and convene with the clinical investigation site personnel appropriate and timely corrective actions.

The first monitoring visit at the site should be conducted as soon as reasonably possible after the first subject(s) has(have) completed the first visit of the investigation. This is to minimise systematic errors done by site and to clarify potential questions before proceeding with enrolment of more subjects.

Additional monitoring will be conducted in accordance with the recruitment rate or if there is a need for more frequent visits upon request from site, clinical monitor, or clinical manager.

The Investigation Site File shall be monitored for 100% completion per the Investigation File Requirement Checklist. Monitoring activities will be documented in a site visit report. A follow up summary describing the observations, including documentation of any deviations and actions required

shall be provided as soon as reasonably possible to the Principal Investigator and/or delegate after the conducted monitoring visit.

All data collected can be directly entered in the eCRF. The monitor will by edit checks ensure that all fields are completed in the eCRF. Monitor will ensure by closely monitoring, that all queries are resolved in a timely manner.

The clinical monitor will have close contact with the sites during the recruitment period to ensure that any concerns, problems, or recruitment challenges are solved with the site in a timely manner.

Only the Principal Investigator, delegated site personnel, the clinical monitor and the sponsor representatives will have access to all the eCRF records.

9.4. Source data verification

Source data is all information in original records, certified copies of original records of clinical findings, observations, or other activities in the clinical investigation, necessary for the reconstruction and evaluation of the clinical investigation. This includes source data initially recorded in an electronic format. A source document is a document in which data collected for a clinical investigation is first recorded.

All documents and data related to the clinical investigation handled by site personnel, shall be produced, and maintained in a way that assures reliability, integrity, control, and traceability, and shall be appropriately stored to provide a complete history.

The Principal Investigator shall ensure the accuracy, attribution, completeness, legibility, and timelines of the data reported to the sponsor in the eCRFs and in all required reports. All printed copies of electronic source documents shall be certified, as indicated by a dated signature by the investigational site personnel at the time the document is printed. Special requirements should be applied to the capture, review, and retention of electronic source data, to ensure reliability, quality, integrity, and traceability.

The data reported in the eCRF shall be derived from source documents and be consistent with these source documents, and any discrepancies shall be explained in writing. The eCRF can serve as the source document and this must be documented on the Source Data Specification Form must be completed at the initiation visit detailing the location of the source data for each data point agreed upon by the Principal Investigator.

Data points for data verification:

- Informed Consent Form
- In- / Exclusion criteria
- AE/ADE/SAE/SADE/DD
- Other

Written informed consent, in- and exclusion criteria and all AE's, ADE's, SAE's, SADE's and DD occurring in the investigation will be 100% verified for timely completion for all subjects enrolled in the investigation.

9.5. Remote monitoring

Remote or centralized monitoring is a remote evaluation carried out by sponsor personnel or representatives (e.g., data management personnel, statisticians, or clinical monitors) at a location other than the site(s) at which the clinical investigations is being conducted. Remote monitoring processes can provide many of the capabilities of on-site monitoring as well as additional capabilities.

In addition to onsite monitoring visits, remote monitoring of the data entered in the eCRF system could be used to achieve the following:

- Conduct activities such as: standard checks of range, consistency, and completeness of data and checks for unusual distribution of data, such as to little variance.
- Special attention will be given in case of frequent data anomalies or errors, protocol deviations/violations or excessive dropouts.
- Augment on-site monitoring by performing monitoring activities that can only be accomplished using centralized processes.
- Monitor data quality through routine review of submitted data in real-time to identify missing data, inconsistent data, data outliers, and potential protocol deviations that may be indictive of systemic and/or significant errors in data collection and reporting at the site.
- Verify source data remotely, provided that both source data and eCRF's can be assessed remotely.
- Conduct aggregate statistical analyses of the study data for plausibility and completeness.
- Conduct analyses of site characteristics, performance metrics (e.g., high screen failure rates, high frequency of eligibility violations, and delays in reporting data), and clinical data to identify early on corrective actions needed for characteristics correlated with poor performance or noncompliance.

10. Statistical considerations

10.1. Statistical design, method, and analytical procedures

The primary objective will be evaluated by analyzing the primary endpoint whereas the analyses of the exploratory endpoints will be used to further evaluate and explore the primary objective. The secondary objective will be evaluated by analyzing the secondary endpoint.

All baseline measurements, endpoints and assessments will be summarized by descriptive statistics and/or listed. Descriptive statistics for continuous variables are presented with N, Mean, SD (standard deviation), Median, Min and Max, where N denotes the number of subjects contributing with non-missing data. For discrete variables, descriptive statistics are presented with N and percentage, where percentage is based on the total number of subjects/observations with non-missing data.

As it is an exploratory study no adjustment for multiple testing will be applied.

All statistical analysis will be performed with SAS (version 9.4/Enterprise Guide version 7.1)

Definition of analysis populations:

The Intention to Treat (ITT), Safety and Per Protocol (PP) populations will be defined at a formal data review meeting before data base lock. As a minimum, the data manager, the clinical manager, the scientific manager, and the statistician will be involved in the classification of subjects according to the below described criteria.

The ITT population (full analysis set) will be constituted by all randomized subjects with valid informed consent who have been exposed to at least one product.

The PP population will constitute a subset of ITT subjects who:

· fulfill the inclusion/exclusion criteria

- have not used other dressings than the investigational test product(s) during the study period
- Have not had a wound infection during the study period
- have not shifted therapy during the study period

Any exclusion of subjects from the ITT/PP populations must be documented.

Invalid individual datapoints may be omitted from the analysis even though the corresponding subject is part of the ITT/PP populations. Any exclusion of data points will be documented

The Safety Population will constitute by subjects who have given informed consent.

All statistical analysis will be based upon the ITT and PP populations, whereas adverse events and device deficiencies will be assessed based on the Safety population.

Considering the data obtained, it may be considered to make additional explorative analysis, based on a subset of ITT/PP populations.

Analysis of the primary endpoint:

The percent wound area reduction (WAR) will be analyzed by an analysis of variance with treatment and wound type (VLU and DFU) as fixed effects and wound area at baseline as covariate.

The mean WAR for each treatment group will be estimated together with the 95% confidence interval. Further, the difference in mean including a 95% confidence interval between the 2 treatments will be estimated.

Analysis of the secondary endpoint:

The secondary endpoint, total cost, will be calculated as the number of products used during the investigational period multiplied by the unit price of the product. Unit price will be extracted from Drug Tarif on the date of Last Patient Out.

This secondary endpoint will be analyzed by comparing the mean cost in the two groups assuming the cost data to be normally distributed. It will be tested on a 2-sided 5% test level if the difference in mean between the two treatments is zero. Further, the mean cost for each treatment will be estimated together with a 95% confidence interval.

Analysis of exploratory endpoints:

Percentage wound depth reduction will be analyzed by the same model as described for the primary endpoint but with wound depth at baseline as covariate.

Similarly, the two endpoints related to EQ-5D-5L (the index score and the VAS score) will be analyzed by an analysis of variance with treatment as a fixed effect and the baseline measure as covariate.

The two endpoints; responder defined as a subject reaching ≥ 30% wound area reduction within the 4-week investigation period (Yes/No) and wound healed during the investigation period (Yes/No) will be analyzed by a logistic regression model with treatment and wound type (VLU or DFU) as fixed effects and wound area at baseline as covariate.

Analysis of safety endpoints:

Adverse events will be listed and summarized, if relevant. Device deficiencies and concomitant medication will be listed.

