5.8. Randomization Procedure

All included subjects that meet the inclusion and exclusion criteria will be randomized to one of two treatment groups. Randomization will be centralized using Medidata RAVE and stratified based on wound type (VLU or DFU).

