6.4. Point of enrolment

A subject is considered enrolled/included in the investigation when written informed consent is obtained.

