6.5. Screening Failures and randomisation failures

Subjects that have signed the informed consent form but fail to comply with inclusion or exclusion criteria are considered screening failures.

A subject can be randomized by mistake e.g., if the investigator realizes that the subject is not eligible after the subject has been randomised. If the subject has not started study treatment and has no data registered on endpoints the subject can be replaced by a new subject if the new subject can complete the investigation within timelines (before last subject last visit and within visit windows).

If a subject is randomized to one product but by mistake gets the opposite product it will be regarded as a randomization failure. As this is an exploratory investigation the statistical analyses will in that case be based on the actual product and not the randomized product.

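### The safety population is defined by consent alone, so subjects who never used a dressing enter the denominator of any pooled adverse-event percentage

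*Combined protocol and SAP*

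**What the plan says.** The population definitions in section 10.1 give one condition for the safety set: "The Safety Population will constitute by subjects who have given informed consent". The same section states that "adverse events and device deficiencies will be assessed based on the Safety population". For efficacy, the ITT set is narrower and does require use of a product: "all randomized subjects with valid informed consent who have been exposed to at least one product".

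Three other rules decide who falls into the safety set:

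- Section 6.4 fixes entry to the study at consent: "A subject is considered enrolled/included in the investigation when written informed consent is obtained".
- Section 6.5 describes a group that consents and goes no further: "Subjects that have signed the informed consent form but fail to comply with inclusion or exclusion criteria are considered screening failures".
- Section 5.8 gives that group no arm, since randomisation is limited to eligible subjects: "All included subjects that meet the inclusion and exclusion criteria will be randomized to one of two treatment groups".

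Section 6.5 also foresees subjects randomised in error who never start treatment. They can be replaced, but nothing removes them from the safety set.

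On outputs, the safety paragraph of section 10.1 has adverse events listed, and summarised if relevant. Device deficiencies are listed only. No layout by arm is given. For discrete variables in general, the "percentage is based on the total number of subjects/observations with non-missing data".

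**The concern.** A safety percentage is normally read as the share of people who used the product and had an event. Here the named set also holds people who used neither product. They cannot have an adverse device effect, which section 18.2 ties to use of the product, yet they count in the denominator.

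The plan applies an exposure condition to efficacy and omits it for safety, so the safety set is wider than the ITT set for no stated reason. The data review meeting does not repair this, because section 10.1 has it classify subjects by the written criteria. Anyone who produces a summary by treatment must then make a choice that the plan does not make: what to do with subjects who have no arm, and with those who have an arm but received no product.

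**Working it through.** **Who is in each set, by the written rules**

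| Subject | Randomised arm | Product used | ITT set | Safety set |
|---|---|---|---|---|
| Screening failure after consent | none | none | no | yes |
| Randomised, never treated | yes | none | no | yes |
| Randomised and treated | yes | yes | yes | yes |

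The first two rows are the whole issue.

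**The plan's own number.** Section 10.2 needs 80 completers and allows 20% dropout: 80/(1 − 0.20) = 100, which matches the stated total. Section 6.2.1 stops recruitment once 100 subjects are included and randomised, so screening failures come on top of the 100. The plan gives no size for the safety set and no expected number of screening failures.

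**Effect on a pooled percentage.** Take 100 exposed subjects, of whom x have an event, and s unexposed subjects with no event.

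- Percentage among exposed: x/100.
- Percentage on the set as defined: x/(100 + s).
- Ratio of the second to the first: 100/(100 + s).

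The value of s is an assumption. An illustrative range, with x = 10:

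| s | Factor | 10.0% among exposed is shown as |
|---|---|---|
| 0 | 1.00 | 10.0% |
| 5 | 100/105 = 0.95 | 10/105 = 9.5% |
| 10 | 100/110 = 0.91 | 10/110 = 9.1% |

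If unexposed subjects do have events, for example from study procedures, the dilution is smaller. The percentage then mixes two groups.

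**Effect within an arm.** Screening failures have no arm, so they drop out of any arm column and do not change either product's rate. A randomised but untreated subject can change one. With 50 per arm (assuming 1:1 allocation; section 10.2 plans equal numbers of completers, but no ratio is stated), one such subject makes the denominator 50 where 49 were exposed. The factor is 49/50 = 0.98.

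**Device deficiencies.** A listing has no denominator, so nothing changes.

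**The case against.** The strongest reply is that consent-based capture fits the rest of the plan. Enrolment is at consent, the adverse-event definition in section 18.1 covers study procedures as well as devices, and section 9.4 verifies events for every enrolled subject. A set that matches the collection period loses no event. This is a sound reason to collect from consent. It is not a reason to use the same set as the denominator, and a separate listing keeps every event.

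The second reply is that few people are involved. Criteria are reviewed at V0, and the V1 list in section 7.2 puts the eligibility check before consent, with randomisation and the first dressing at the same visit. This stands, and it is why s is probably small. It does not make s zero: baseline wound size and depth are listed after consent, eligibility depends on depth and diameter, and section 9.5 names screen failure rates as something to monitor.

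The third reply is that the non-missing rule may already drop some of these subjects, since the V1 adverse-event review is listed after dressing application. That is possible, but the plan does not say whether a subject with no adverse-event entry counts as missing or as event-free.

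A reader might also infer more than the text supports:

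- *That both products would look safer.* Subjects with no arm cannot enter either product's denominator. Screening failures can dilute only a pooled figure.
- *That device-deficiency rates are diluted.* No such rate is planned.
- *That a table by arm cannot be built.* It can, by leaving out subjects without an arm. The plan just does not say so, and it specifies no such table.
- *That the dilution is large.* A factor of 0.80 needs 25 unexposed subjects per 100 exposed, and nothing in the documents points to that.

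**Conclusion.** The point holds in a limited form. As written, the safety set includes consented subjects who used no dressing. A pooled adverse-event percentage is then too low by the factor 100/(100 + s): 0.95 for an assumed s of 5. This rests on no events among the unexposed, on their being counted as non-missing, and on a value of s that the documents do not give.

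No study conclusion turns on it. The pass/fail criteria in section 10.4 use wound area and cost only. The anticipated device-effect rates in Table 5 run from 0 to 0.13%; read as per subject, 0.13% of 100 is 0.13 expected cases, too few for the denominator to matter. This is a cheap improvement to a stated rule, not a threat to the results.

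**What to change.** Replace the safety sentence in section 10.1 so that the set is all subjects who had at least one study dressing applied, grouped by the dressing received. This brings safety into line with the exposure condition already used for ITT, and with section 6.5, which analyses a subject given the opposite product by the product actually used.

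Add that events continue to be collected from consent, and that any event in a consented but unexposed subject is listed separately.

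The cost is this edit, one extra listing, and stated adverse-event percentages that are slightly higher. It needs no new data and no change to the sample size.
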